#### **6.6.1.1 Medical Outcome Short Form Health Survey (SF-36) Version 2 (Acute Form)**

The SF-36 is a widely used and extensively studied instrument to measure health-related quality of life among healthy patients and patients with acute and chronic conditions. It consists of eight subscales that can be scored individually: Physical Functioning, Role-Physical, Bodily Pain, General Health, Vitality, Social Functioning, Role-Emotional, and Mental Health ([Ware and Sherbourne 1992](#)). Two overall summary scores, the Physical Component Summary (PCS) and the Mental Component Summary (MCS) also can be computed ([McHorney et al 1993](#)). The SF-36 has proven useful in monitoring general and specific populations, comparing the relative burden of different disease, differentiating the health benefits produced by different treatments, and in screening individual patients.

[figure not shown]
[figure not shown]
[figure not shown]

The purpose of the SF-36 in this study is to assess the health-related QoL of patients. Given the acute nature of this disease, version 2, with a 1-week recall period, will be used in this study.

#### **6.6.1.2 Ankylosing Spondylitis Quality of Life (ASQoL)**

The ASQoL is a self-administered questionnaire designed to assess health-related quality of life in adult patients with Ankylosing Spondylitis. The ASQoL contains 18 items with a dichotomous yes/no response option. A single point is assigned for each "yes" response and no points for each "no" response resulting in overall scores that range from 0 (least severity) to 18 (highest severity). As such, lower score indicate better quality of life. Items include an assessment of mobility/energy, self-care and mood/emotion. The recall period is "at the moment," and the measure requires approximately 6 minutes to complete.

The purpose of the ASQoL is to assess the disease specific QoL of patients in this study.

### **6.6.3 HLA-B27**

A blood sample to analyze Human Leukocyte Antigen-B27 (HLA-B27) will be obtained from all patients at baseline.

Details on the collection, handling and shipment of the sample to the central laboratory will be provided to investigators in the laboratory manual.

### **6.6.4 Resource utilization**

No measures of Healthcare Resource Utilization (RU) will be collected in the study.

### **6.6.5 Pharmacokinetics (PK)**

PK samples will be obtained for all patients. Secukinumab concentrations will be assessed in serum. The PK samples will be collected pre-dose at scheduled visits as indicated in [Table 6-1](#). The Pharmacokinetics Sample Log can be found in the [Appendix 2](#). All blood samples will be taken by direct venipuncture in a forearm vein.

The actual sample collection date and exact time will be entered on the PK blood collection summary page in the eCRF.

## **PK sample handling, labeling and shipment instructions**

Laboratory manuals will be provided by the central laboratory with detailed information on sample collection, sample handling and shipment.

Tubes and labels will be provided by the central laboratory with study/sample type information pre-printed on the label.

## **Analytical methods**

An ELISA method will be used for bioanalytical analysis of secukinumab in serum, with an anticipated lower limit of quantification (LLOQ) of 80 ng/mL. The detailed method description to assess secukinumab concentration will be described in the bioanalytical raw data of the study and in the respective Bioanalytical Data Report.

# **7 Safety monitoring**

## **7.1 Adverse events**

AE is any untoward medical occurrence (i.e., any unfavorable and unintended sign [including abnormal laboratory findings], symptom or disease) in a subject or clinical investigation subject *after providing written informed consent* for participation in the study. Therefore, an AE may or may not be temporally or causally associated with the use of a medicinal (investigational) product.

The occurrence of adverse events should be sought by non-directive questioning of the patient at each visit during the study. Adverse events also may be detected when they are volunteered by the patient during or between visits or through physical examination, laboratory test, or other assessments.

Abnormal laboratory values or test results constitute adverse events only if they fulfill at least one of the following criteria:

- they induce clinical signs or symptoms,
- they are considered clinically significant,
- they require therapy.

Clinically significant abnormal laboratory values or test results should be identified through a review of values outside of normal ranges/clinically notable ranges, significant changes from baseline or the previous visit, or values which are considered to be non-typical in patient with underlying disease. Investigators have the responsibility for managing the safety of individual patient and identifying adverse events. Alert ranges for labs and other test abnormalities are included in [Appendix 1](#).

Adverse events should be recorded in the Adverse Events CRF under the signs, symptoms or diagnosis associated with them, accompanied by the following information.

- the severity grade
  - mild: usually transient in nature and generally not interfering with normal activities
  - moderate: sufficiently discomforting to interfere with normal activities
  - severe: prevents normal activities

- its relationship to the study treatment (no/yes)
- its duration (start and end dates), or if the event is ongoing, an outcome of not recovered/not resolved should be reported.
- whether it constitutes a serious adverse event (SAE)
- action taken regarding study treatment
- whether other medication or therapies have been taken (concomitant medication/non-drug therapy)
- its outcome (not recovered/not resolved; recovered/resolved; recovering/resolving, recovered/resolved with sequelae; fatal; or unknown)

Once an adverse event is detected, it should be followed until its resolution or until it is judged to be permanent, and assessment should be made at each visit (or more frequently, if necessary) of any changes in severity, the suspected relationship to the study drug, the interventions required to treat it, and the outcome.

Information about common side effects already known about the investigational drug can be found in the Investigator Brochure (IB) or will be communicated between IB updates in the form of Investigator Notifications. This information will be included in the patient informed consent and should be discussed with the patient during the study as needed.

The investigator should also instruct each patient to report any new adverse event (beyond the protocol observation period) that the patient, or the patient's personal physician, believes might reasonably be related to study treatment. This information should be recorded in the investigator's source documents, however, if the AE meets the criteria of an SAE, it must be reported to Novartis.

## **7.2 Serious adverse events**

### **7.2.1 Definition of SAE**

An SAE is defined as any adverse event (appearance of (or worsening of any pre-existing) undesirable sign(s), symptom(s) or medical conditions(s) which meets any one of the following criteria:

- is fatal or life-threatening
- results in persistent or significant disability/incapacity
- constitutes a congenital anomaly/birth defect
- requires inpatient hospitalization or prolongation of existing hospitalization, unless hospitalization is for:
  - routine treatment or monitoring of the studied indication, not associated with any deterioration in condition (specify what this includes)
  - elective or pre-planned treatment for a pre-existing condition that is unrelated to the indication under study and has not worsened since signing the informed consent
  - treatment on an emergency outpatient basis for an event not fulfilling any of the definitions of a SAE given above and not resulting in hospital admission
  - social reasons and respite care in the absence of any deterioration in the patient's general condition

- is medically significant, i.e. defined as an event that jeopardizes the patient or may require medical or surgical intervention.

All malignant neoplasms will be assessed as serious under “medically significant” if other seriousness criteria are not met.

Life-threatening in the context of a SAE refers to a reaction in which the patient was at risk of death at the time of the reaction; it does not refer to a reaction that hypothetically might have caused death if more severe (see Annex IV, ICH-E2D Guideline).

Medical and scientific judgment should be exercised in deciding whether other situations should be considered serious reactions, such as important medical events that might not be immediately life threatening or result in death or hospitalization but might jeopardize the patient or might require intervention to prevent one of the other outcomes listed above. Examples of such events are intensive treatment in an emergency room or at home for allergic bronchospasm, blood dyscrasias or convulsions that do not result in hospitalization or development of dependency or abuse (see Annex IV, ICH-E2D Guideline).

Any suspected transmission via a medicinal product of an infectious agent is also considered a serious adverse reaction.

All AEs (serious and non-serious) are captured on the CRF, SAEs also require individual reporting to DS&E as per [Section 7.2.2](#).

## 7.2.2 SAE reporting

To ensure patient safety, every SAE, regardless of causality, occurring after the patient has provided informed consent and until 30 days following the last administration of study treatment if there are post-treatment follow-up visits with no required procedures must be reported to Novartis within 24 hours of learning of its occurrence. Any SAEs experienced after the 30 days period should only be reported to Novartis if the investigator suspects a causal relationship to study treatment.

Recurrent episodes, complications, or progression of the initial SAE must be reported as follow-up to the original episode, regardless of when the event occurs. This report must be submitted within 24 hours of the investigator receiving the follow-up information. An SAE that is considered completely unrelated to a previously reported one should be reported separately as a new event.

Information about all SAEs (*either initial or follow up information*) is collected and recorded on the paper Serious Adverse Event Report Form. The investigator must assess the relationship to *each specific component of study treatment (if study treatment consists of several drugs)* complete the SAE Report Form in English, and send the completed, signed form by fax within 24 hours after awareness of the SAE to the local Novartis Drug Safety and Epidemiology Department. The telephone and fax number of the contact persons in the local department of Drug Safety and Epidemiology, specific to the site, are listed in the investigator folder provided to each site. The original copy of the SAE Report Form and the fax confirmation sheet must be kept with the case report form documentation at the study site. Follow-up information should be provided using a new paper SAE Report Form stating that this is a follow-up to a previously reported SAE

Follow-up information provided should describe whether the event has resolved or continues, if and how it was treated, whether the treatment code was broken or not and whether the patient continued or withdrew from study participation. Each re-occurrence, complication, or progression of the original event should be reported as a follow-up to that event regardless of when it occurs.

If the SAE is not previously documented in the Investigator's Brochure or Package Insert (new occurrence) and is thought to be related to the investigational treatment a Drug Safety and Epidemiology Department associate may urgently require further information from the investigator for Health Authority reporting. Novartis may need to issue an Investigator Notification (IN) to inform all investigators involved in any study with the same investigational treatment that this SAE has been reported. Suspected Unexpected Serious Adverse Reactions (SUSARs) will be collected and reported to the competent authorities and relevant ethics committees in accordance with EU Guidance 2011/C 172/01 or as per national regulatory requirements in participating countries.

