### **5.2 Treatment arms**

This trial is an open label, one arm study. All patients will be treated with secukinumab 150 mg.

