### **5.5.9      Discontinuation of study treatment**

Patients may voluntarily discontinue study treatment for any reason at any time.

They may be considered discontinued if they state an intention to withdraw, fail to return for visits, or become lost to follow-up for any other reason.

If premature discontinuation occurs for any reason, the investigator must make every effort to determine the primary reason for a patient's premature discontinuation from the study and record this information on the appropriate Study Phase Completion eCRF.

Patients who discontinue study should undergo an end of treatment visit (corresponds to the last visit for the patient's current period of treatment: e.g., Week 24, Week 52) at 4 weeks after last study treatment and then also return after an additional 8 weeks for a final follow-up visit, corresponding to Week F60 (12 weeks after last study treatment; see [Table 6-1](#)). The

final follow-up visit should be performed before any new treatment is initiated. For patients who are lost to follow-up (i.e., those patients whose status is unclear because they fail to appear for study visits without stating an intention to withdraw from the study), the investigator should show "due diligence" by documenting in the source documents steps taken to contact the patient, e.g., dates of telephone calls, registered letters, etc.

Patients who are prematurely discontinued from the study will not be replaced.

Study treatment must be discontinued under the following circumstances:

- Withdrawal of informed consent
- Emergence of the following adverse events:
  - a. Any severe or serious adverse event that is not compatible with administration of study medication, including adverse events that require treatment with prohibited co-medication
  - b. Onset of lymphoproliferative disease or any malignancy except for treated basal cell carcinoma, treated actinic keratoses, treated *in situ* carcinoma of the cervix or non-invasive malignant colon polyps which are being or have been removed
  - c. Life-threatening infection
  - d. Any laboratory abnormalities that in the judgment of the investigator are clinically significant and are deemed to place the patient at a safety risk for continuation in the study (A general guidance on clinically notable laboratory values is provided in [Appendix 1](#)).
  - e. Pregnancy
  - f. Use of any biologic immunomodulating agent except secukinumab

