### **5.5.13 Study completion and post-study treatment**

A patient will be considered to have completed the study if he/she received a maximum of 48 weeks of study treatment and upon completion of the scheduled study assessments and procedures up to and including Week F60.

Information on the patient's completion or discontinuation of the study and the reason for discontinuation of the study will be recorded on the appropriate Study Phase Completion eCRF page.

The investigator must provide follow-up medical care for all patients who are prematurely withdrawn from the study, or must refer them for appropriate ongoing care. This care may include initiating another treatment outside of the study as deemed appropriate by the investigator. This treatment may be any non-biologic treatment. In case of a biologic treatment, a waiting period of 12 weeks after the last study treatment before initiating the treatment is recommended.

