## 13.2 Appendix 2: Blood collection logs

**Table 13-2 Blood collection log for immunogenicity**

Week	Timepoint	Volume	IG Sample number
BSL	0 (pre-dose)	2 ml	201
Week 16	0 (pre-dose)	2 ml	202
Week 24	0 (pre-dose)	2 ml	203
Week 52	672 h (post-dose)	2 ml	204
Week 60	2016 h (post-dose)	2 ml	205

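### Does Protocol Section 7.2.2 leave 24-hour SAE reporting without an end, because its 30-day limit carries a condition that Week F60 does not meet?

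*Protocol*

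**What the plan says.** The first paragraph of Protocol Section 7.2.2 sets the period for 24-hour, all-causality SAE reporting. It runs from informed consent "until 30 days following the last administration of study treatment if there are post-treatment follow-up visits with no required procedures". The following sentence reads: "Any SAEs experienced after the 30 days period should only be reported to Novartis if the investigator suspects a causal relationship to study treatment". The third paragraph tells the investigator to complete the form and "send the completed, signed form by fax within 24 hours after awareness of the SAE".

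The trial has one post-treatment follow-up visit, F60. Section 3.1 places it 12 weeks after the last dose for every patient. Section 5.5.9 brings patients who stop early back for a "final follow-up visit, corresponding to Week F60 (12 weeks after last study treatment"). Section 5.5.13 makes study completion depend on "completion of the scheduled study assessments and procedures up to and including Week F60". Tables 13-2 and 13-3 each schedule a Week 60 blood sample at "2016 h (post-dose").

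Two other periods bear on the question. Protocol Section 9.5.3 and SAP Section 2.8.1 count adverse events as treatment-emergent up to 84 days after the last dose. Protocol Section 6 asks for a safety contact during the 30 days after the last study visit.

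**The concern.** The 30-day limit is written as conditional on follow-up visits that require nothing of the patient. F60 requires blood samples and assessments, so the condition is not met for anyone. Taken literally, the protocol then gives an all-causality reporting limit for a situation that does not arise, and none for the situation that does.

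A safety obligation measured in hours should have a clear end. If one site stopped at day 30 and another went on to F60, an SAE judged unrelated and first noticed at F60 would reach the sponsor within a day from one site and only through the CRF from the other. Day 30 also ends well before the 84-day treatment-emergent period and the safety contact after the last visit, which makes the gap look larger than a drafting matter.

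**Working it through.** **1. Is the condition met?** No. Section 5.5.13 ties completion to procedures at F60, Tables 13-2 and 13-3 list samples there, and SAP Section 2.1.2 refers to F60 safety assessments. The clause does not fit this trial.

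**2. Calendar.** SAP Table 2-1 numbers scheduled days as 7 × week + 1.

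- Last dose, Week 48: 7 × 48 + 1 = day 337.
- F60: 7 × 60 + 1 = day 421.
- The protocol's own figure reproduces: 2016 h ÷ 24 = 84 days, and 421 − 337 = 84 days.
- Day-30 limit: 337 + 30 = day 367, two days after the Week 52 visit (day 365).

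**3. Stretch on which the readings differ, up to F60.** Post-dose days 31 to 84 are study days 368 to 421 for a completer: 84 − 30 = 54 days.

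- Share of a completer's time from first dose to F60: 54 ÷ 421 = 12.8%.
- For 30 patients who all complete: 30 × 54 = 1,620 patient-days; 1,620 ÷ 365.25 = 4.4 patient-years.
- Total for the same 30: 30 × 421 = 12,630 patient-days; 12,630 ÷ 365.25 = 34.6 patient-years.

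The documents give no SAE rate, so I do not turn this into an event count.

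**4. What differs on post-dose days 31 to 84.**

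| Item | Day-30 reading | Literal reading |
|---|---|---|
| 24-hour notice of a new SAE not suspected to be related | Not required | Required |
| CRF entry of that SAE (Section 7.2.1; Table 6-1 footnote 7) | Yes | Yes |
| Counted as treatment-emergent (Section 9.5.3; SAP 2.8.1) | Yes | Yes |
| Suspected-related SAE reported to the sponsor | Yes | Yes |
| Follow-up of an SAE already reported (Section 7.2.2) | Yes | Yes |
| SUSAR handling (Section 7.2.2) | Unchanged | Unchanged |
| SAE during pregnancy (Section 7.5) | Reported | Reported |

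Only the first row differs. The table row that carries footnote 7 was not legible in the text available to me, so for CRF capture I rely on the footnote itself and on Section 7.2.1.

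**5. Is the literal reading a real competitor?** It needs a general reporting duty that survives when the condition fails.

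- Section 7.2.1 says SAEs need individual reporting, but sends the reader to Section 7.2.2 for how. It adds no independent duty.
- The third paragraph of Section 7.2.2 covers the form and the speed of sending it, not which SAEs qualify.
- Section 7.1 concerns events after the observation period that are believed related to treatment. That is consistent with a causality-limited rule later on.
- The second sentence of Section 7.2.2 has no condition of its own and names the 30-day period. It is the only day count for SAE reporting in either document.

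A site applying the section therefore arrives at day 30.

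**6. The other periods.** For a completer the Section 6 contact extends to day 421 + 30 = 451, which is 451 − 367 = 84 days beyond the day-30 limit. It is a duty to contact the patient and sets no notification period. The 84-day treatment-emergent period is an analysis rule. Nothing in the documents requires either to equal the notification period, so the differences are not contradictions.

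**The case for a change.** The best case for acting is this. The second sentence refers back to a period that was itself conditional, so strictly it cannot supply a limit on its own. Two careful sites could reach different answers. On the day-30 reading, the investigator's view of causality alone decides whether an SAE first seen at F60 is notified within 24 hours. Sections 8.4 and 8.5 provide no monitoring or adjudication committee, so site notice is the main rapid route to the sponsor. The repair would take a sentence or two.

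Part of this stands: the clause is wrong for this trial and would be better absent. The rest carries little weight. Reliance on the investigator's causality judgement after a fixed date is what the second sentence says in plain terms; it is a choice about length, not a product of the faulty clause. CRF review (Section 8.3) and full source verification of SAE documentation (Section 8.1) still bring unsuspected events to the sponsor, only later. Nor is the repair quite as light as it sounds, because Section 11.1 requires a written amendment with sponsor and ethics approval, and Health Authority approval where required. SAP Sections 1.1 and 2.14 show that the Week 24 analysis had already been done.

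The same section asks "whether the treatment code was broken or not", although Section 5.2 states: "This trial is an open label, one arm study". That has no bearing on the reporting limit, and Sections 5.4 and 5.5.12 mark blinding and code-breaking as not applicable. It does support the view that Section 7.2.2 carries standard text that was not trimmed for this design.

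**Conclusion.** The concern is right about the wording and does not call for a change. The condition attached to the 30-day limit is a clerical remnant. The unconditional sentence after it gives sites one workable rule, and no other SAE reporting limit competes with it.

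Up to F60, the effect is confined to how quickly the sponsor hears of new SAEs not suspected to be related, over 54 days per patient and at most 4.4 of 34.6 patient-years. Those totals assume that all 30 planned patients receive the Week 48 dose and attend F60 on schedule. No estimate, table or efficacy or safety conclusion depends on which reading a site adopts, provided that SAEs are entered on the CRF as Section 7.2.1 requires.

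Rewording would bring no clear gain. If the sponsor confirmed day 30, practice would stay as it is. If it chose a later end, that would be a new design decision that nothing in the documents compels.
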